5.9.2. SUBJECT CLASSIFICATION

- Enrolled subject- Any participant who signs the informed consent form.
- Screen Failure subject- Any participant who signs the consent form but is found to not meet eligibility criteria.
- Intent subject- Any participant who signs the consent form, met the eligibility criteria but did not have the VERAFEYE Imaging Catheter inserted into the body.
- Attempt subject- Any participant who signs the consent form, met the eligibility criteria, did have the VERAFEYE Imaging Catheter inserted into the body but did not undergo the ablation/LAA/ASD closure procedure per this study protocol.
- Procedure subject - Any participant who undergoes the ablation/LAA/ASD closure procedure with the VERAFEYE System as imaging system per this study protocol.

These subjects are followed in accordance with the Follow-Up schedule and data will be included in all study analyses.

[figure not shown]
- Withdrawn subject - A participant who chooses to or is withdrawn from the study.
- Lost-to-follow up subject - A participant who cannot be reached anymore after 3 attempts.

Enrolment will be considered as complete when 20 procedure subjects have been enrolled.

The Figure below shows the subject classifications.

**LUMINIZE_CLINICAL PROTOCOL**Document ID: VER-DOC-527
Controlled Document: VER-SIGN-3084TEMPLATE:
ONEPROJECTS/SIGN-267

Version: 4.0

Project: VERAFYE (VER)
Date: 22-Nov-2024 14:16:10
Page: 22 / 51**Figure 5: Subject Classifications****5.9.3. END OF STUDY**

Individual study subject participation will end when the last subject follow-up visit is completed; when the subject withdrew or was withdrawn from the study or when the subject is considered as lost-to-follow up.

The study will be considered as complete when the last subject's follow up visit occurs or when subjects are no longer being considered for participation. Routine management and standard practice of care will continue for the subjects who have completed the study.

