- Presence of intramural thrombus, tumor, or other abnormality that precludes vascular access, catheter introduction, or manipulation
- Active coronary ischemia, significant valvular heart disease, or hemodynamically significant congenital cardiac abnormality

EC4: Body mass index (BMI) > 40 kg/m²

EC5: Body weight < 50kg

EC6: Pregnant women or women who plan to become pregnant during the course of their participation in the study (women should either be of non-childbearing potential at the time of enrolment (as documented in the medical file) or have a negative pregnancy test within the previous 7 days prior to the ablation, or LAA/ASD closure procedure)

EC7: Life expectancy less than 12 months

EC8: Subjects who are currently enrolled in another study

Imaging Exclusion Criteria

IEC1: Subjects with a thrombus or pericardial effusion detected in the LA/LAA during standard of care imaging.

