5.10.3.3. Procedure Workflows**Pre-Procedural Imaging**

Pre-procedural imaging will be performed per hospital standard of care to assess the anatomy and to exclude the presence of thrombus. If an intracardiac thrombus is visualized, the procedure will be aborted and the subject will be withdrawn from the study. Pre-procedural imaging may be collected at baseline or on the day of the procedure.

Intra-Procedural Imaging

VERAFEYE imaging data from the right atrium will be obtained during the ablation, or LAA/ASD closure procedure. This procedure is to be performed using a commercially available ablation catheter or LAA/ASD closure device. The choice of the ablation catheter, or LAA/ASD closure device is at the operator's discretion. This ablation, or LAA/ASD closure procedure will be performed according to standard of care. The ablation, or LAA/ASD closure procedure will not be guided by the data collected from the VERAFEYE System, the physician is to adhere to a standard workflow and rely on standard imaging and diagnostic tools, as applicable. In order to prevent artifact between the VERAFEYE System and the standard of care echocardiography imaging (intracardiac echocardiography (ICE) transesophageal echocardiography (TEE)), the VERAFEYE imaging has to be frozen during standard of care echocardiography imaging and vice versa.

No concomitant procedures are allowed to be performed at the time of the ablation, or LAA/ASD closure procedure under this protocol. It is also not allowed to combine an ablation procedure with an LAA/ASD closure procedure or to combine an LAA closure procedure with an ASD closure procedure.

It is recommended that the following views with the VERAFEYE Imaging Catheter be obtained in order to visualize the major anatomical structures, as well as third party devices.

RA (typical AFL) Ablation

- Home view
- A variety of anatomical views from different VERAFEYE Imaging Catheter locations, at the discretion of the investigator
- View to visualize mapping* and/or ablation catheter

*If used, per hospital standard's of care

**LUMINIZE_CLINICAL PROTOCOL**Document ID: VER-DOC-527
Controlled Document: VER-SIGN-3084TEMPLATE:
ONEPROJECTS/SIGN-267

Version: 4.0

Project: VERAFYE (VER)
Date: 22-Nov-2024 14:16:10
Page: 26 / 51**LA (AF) Ablation**

- Home view
- A variety of anatomical views from different VERAFYE Imaging Catheter locations, at the discretion of the investigator
- Transseptal puncture view

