5.10.3.4. Procedural Data Collection

The following data *related to the procedure* will be collected:

- Date of procedure
- Pre-procedural imaging per hospital's standard of care, if performed at procedure visit*

**LUMINIZE_CLINICAL PROTOCOL**Document ID: VER-DOC-527
Controlled Document: VER-SIGN-3084TEMPLATE:
ONEPROJECTS/SIGN-267

Version: 4.0

Project: VERAFEYE (VER)
Date: 22-Nov-2024 14:16:10
Page: 27 / 51

- Intra-procedural imaging per hospital's standard of care, as applicable
- Identification of all investigational study devices
- Identification of non-study devices
- Rhythm at the beginning of the procedure (by means of a 12-lead ECG)
- Method of delivering sedation or anesthesia for the procedure
- Method of access to left atrium: single or double transseptal
- Performance of the study device
- Procedural outcome details
 - Ablation procedures: successful isolation of CTI (typical AFL) or PVs (AF)
 - LAA/ASD closure procedures: successful deployment of closure device

At the end of the procedure, the following information will be collected:

- Total procedure time, defined as time elapsed from time first access sheath insertion into the subject until the last catheter removed
- Total fluoroscopy time and dose
- Total time VERAFEYE imaging catheter was in the body, defined as time elapsed from inserting the VIC into the subject until the time of VIC removal from the subject
- Rhythm at end of case (by means of a 12-lead ECG)
- Physical assessment
- Concomitant procedures, if applicable
- Changes in Medication Regimen
- Adverse Events if applicable
- Device Deficiencies
- Protocol Deviations, if applicable
- The data collected through the System Console will be saved and stored to external media, as provided by the sponsor

*Standard of care imaging data will be saved and stored to external media, as provided by the sponsor

After the completion of the procedure, the images collected with the VERAFEYE System during the procedure may be reviewed with the physician and the physician will be asked to rate the performance of the system by means of a questionnaire.

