5.10.4. POST-PROCEDURE VISIT

The Post-Procedure visit is applicable for attempt subjects and procedure subjects.

The post-procedure visit will occur per standard of care but not to exceed 2 days from the end of the study procedure. The data collection requirements of the post procedure visit are outlined below:

- Date of visit
- Physical assessment (incl. vital signs and 12-lead ECG)
- Changes in Medications Regimen

**LUMINIZE_CLINICAL PROTOCOL**Document ID: VER-DOC-527
Controlled Document: VER-SIGN-3084TEMPLATE:
ONEPROJECTS/SIGN-267

Version: 4.0

Project: VERAFYE (VER)
Date: 22-Nov-2024 14:16:10
Page: 28 / 51

- Adverse Events, if applicable
- Protocol Deviations, if applicable

5.10.5. 7-DAY FOLLOW-UP

The 7-day follow-up is applicable for attempt subjects and procedure subjects.

If the patient was discharged prior to the day 7 follow-up, a telephone contact will occur. If the patient is still hospitalized at the time of the day 7 follow-up, the 7 days follow-up will be performed as an in-hospital visit. The data collection at the day 7 follow-up includes:

- Date of contact (visit/telephone call)
- Changes in Medication Regimen
- Adverse Events, if applicable
- Protocol Deviations, if applicable

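### Section 5.9.2 ties the Attempt class to eligibility as well as catheter insertion, so a device-exposed subject found ineligible after insertion, with the procedure not completed, has no scheduled safety contact

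*Combined protocol and SAP*

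**What the plan says.** Section 5.9.2 sorts consented subjects into classes. Screen Failure is "Screen Failure subject- Any participant who signs the consent form but is found to not meet eligibility criteria". It has no time limit and no condition on whether the VIC was inserted. An Attempt subject is one who consented and "met the eligibility criteria, did have the VERAFEYE Imaging Catheter inserted into the body but did not undergo the ablation/LAA/ASD closure procedure". A Procedure subject is "Any participant who undergoes the ablation/LAA/ASD closure procedure with the VERAFEYE System as imaging system per this study protocol", with no eligibility condition.

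Class decides scheduled follow-up. Section 5.10.4 states: "The Post-Procedure visit is applicable for attempt subjects and procedure subjects". Section 5.10.5 states: "The 7-day follow-up is applicable for attempt subjects and procedure subjects". No other class is named in either place.

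The imaging exclusion in Table 2 (Section 5.8), repeated in the synopsis, reads "IEC1: Subjects with a thrombus or pericardial effusion detected in the LA/LAA during standard of care imaging". It gives no point after which it stops applying. Section 5.10.3.3 allows pre-procedural imaging at baseline or on the procedure day, and says of the procedure itself that "the VERAFEYE imaging has to be frozen during standard of care echocardiography imaging and vice versa". Section 5.10.3.4 lists among the data to be collected "Intra-procedural imaging per hospital's standard of care, as applicable".

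**The concern.** In a feasibility study of an investigational catheter, the natural trigger for safety follow-up is whether the catheter entered the body. Section 5.9.2 adds a second condition, eligibility. A subject can meet the first condition and fail the second, and the visit rules then assign that subject nothing.

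At stake is the day 0 to 2 visit and the day 7 contact in a person who was exposed to the device and whose procedure was not completed. Without them, a later event such as an access-site or embolic complication would come to light only if the subject or the treating team raised it. There is also a consistency problem: two sites could put the same subject in different classes and follow that subject differently.

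**Working it through.** The plan states no figure on this point, and Section 5.7 says that the 40 subjects have no statistical basis. The check is therefore one of logic.

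**Step 1. Apply each class to the case: VIC inserted, procedure not completed, a criterion then found not to be met.**

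- Intent: no. It requires that the VIC was not inserted.
- Attempt: no. It requires that eligibility was met.
- Procedure: no. The ablation or closure was not carried out.
- Screen Failure: yes, on its wording.
- Withdrawn: only if the subject leaves or is taken out of the study. Section 5.9.4 then ends further data collection.

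Sections 5.10.4 and 5.10.5 name only Attempt and Procedure, so 0 of the 2 scheduled post-exposure contacts apply.

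**Step 2. Ask which criteria could produce the case.**

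- EC3 includes an abnormality that prevents catheter introduction or manipulation. This can come to light while a catheter is being handled. It was present beforehand, so the subject never met eligibility.
- EC1 lists events and procedures in the preceding 6 months. One of these could surface in the records after insertion.
- IEC1 depends on how it is read. Baseline imaging is recorded only if it was done at baseline (Section 5.10.2), and imaging may be done on the procedure day. IEC1 therefore cannot always be settled at baseline, and no closing point is given. If it is read as still open while standard echocardiography alternates with VERAFEYE imaging, a finding after insertion could trigger it. A finding on VERAFEYE imaging alone could not, because IEC1 refers to standard of care imaging.

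**Step 3. Ask who is not affected.** A subject who completes the procedure with the VERAFEYE System is a Procedure subject whatever is found about eligibility, and keeps both contacts. The Screen Failure wording also fits that subject, so the classes overlap, but follow-up is not lost.

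**Step 4. Trace thrombus separately.** Under its pre-procedural imaging heading, Section 5.10.3.3 sends a subject with a visualized intracardiac thrombus to withdrawal, and Section 5.9.4 then stops data collection. If that sentence were applied after insertion, follow-up would end by this route and not through Screen Failure. The sentence does not mention effusion.

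**Step 5. Scale, for illustration only.** Assume 40 Procedure subjects and one subject of this kind.

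- Share of exposed subjects without scheduled contact: 1/(40 + 1) = 2.4%.
- If that subject had a later event that was never detected, and no other subject had one, the count would be 0/40. The exact 95% upper limit is 1 − 0.025^(1/40) = 8.8%. If it was detected, the count would be 1/41 = 2.4% (exact 95% interval 0.06% to 12.9%).
- The chance of at least one such subject in 40 is 1 − (1 − p)^40. The documents give no p. Assumed values of 0.5%, 1%, 2% and 3% give 18%, 33%, 55% and 70%.

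**The case against.** A reader might infer that any effusion or thrombus first seen after insertion turns a complication into a screening exclusion and biases the complication description downward. The documents do not support that, for several reasons.

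- Eligibility verification is scheduled at baseline (Section 5.10.2 and Table 3), and the Attempt definition speaks of eligibility in the past tense. Pericardial effusion is a listed potential adverse event in Tables 4 and 5. A new effusion after insertion therefore reads more naturally as an anticipated event in an Attempt subject, who keeps both contacts.
- Thrombus is directed to withdrawal, not to Screen Failure.
- Section 5.13.2 requires reportable events to be reported for all participants after enrolment, whatever their class. The index event is not lost.
- There is no safety endpoint and no hypothesis test, and analysis is descriptive. The protocol names no exposed analysis group, and its sentence on inclusion in all analyses follows the Procedure definition. Attempt status would restore the contacts but would not clearly bring the subject into the analyses.
- Figure 5, on subject classifications, is not available here and may show an order of assignment.

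These points dispose of the broad reading. They do not close the gap in Section 5.9.2. The past-tense argument fails for a condition that was present before insertion, as with EC1 or EC3. Event reporting does not replace a scheduled contact that looks for later events. Written definitions should not depend on a figure to settle which class applies.

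**Conclusion.** The gap holds in a limited form. As written, a subject with the VIC inserted, an uncompleted procedure and an eligibility failure found afterwards is outside both classes that receive scheduled follow-up. This follows directly for a pre-existing EC1 or EC3 condition. For IEC1 it holds only if that criterion is read as still open during the procedure, which the text neither says nor rules out.

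The loss per subject is both scheduled contacts, and with them the planned detection of later events. The number of subjects is likely to be small but cannot be estimated from the documents. The 1/41 and the intervals above rest on an assumed single case and are not evidence of bias. The point is worth correcting because a written rule decides who gets safety follow-up, and the change is short.

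**What to change.** 1. In Section 5.9.2, limit Screen Failure to consented subjects who fail eligibility and in whom the VIC was not inserted.
2. Define Attempt as consented, VIC inserted and procedure not completed, regardless of any eligibility failure found later. Record that failure as a protocol deviation.
3. Make Figure 5 agree.
4. In the synopsis and Table 2, state the point at which IEC1 is assessed for classification purposes.
5. Reconcile Sections 5.8, 5.9.2, 5.9.4, 5.10.3.3, 5.10.4 and 5.10.5 so that every subject with the VIC inserted has a defined class and defined safety follow-up, subject to consent. This includes a subject withdrawn for thrombus after insertion.
6. Record findings made after insertion as adverse events only where they meet the definition in Table 6 and the rule in Section 5.13.2 on pre-existing conditions. A blanket instruction to record all of them would conflict with that rule, since a thrombus first seen after insertion may have been there before.

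These are changes to classification and data collection; clinical management is unchanged. The cost is the wording, one figure, and at most one post-procedure visit and one call for each of a few extra subjects.

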5.1. CONTACT INFORMATION

Position	Details
Sponsor	LUMA Vision Ltd. [name]
Coordinating Principal Investigator	[name]. [name] [name], FESC, FEHRA Mater Private Network Heart & Vascular Centre [name]

**LUMINIZE_CLINICAL PROTOCOL**Document ID: VER-DOC-527
Controlled Document: VER-SIGN-3084TEMPLATE:
ONEPROJECTS/SIGN-267

Version: 4.0

Project: VERAFYE (VER)
Date: 22-Nov-2024 14:16:10
Page: 7 / 51

	Ireland Email: [contact]
Clinical Manager	[name] [contact] [contact]
Clinical Research Engineer	[name] [contact] [contact]

5.2. PROTOCOL SYNOPSIS**Study title:** LUMINIZE: Luma Vision's feasibility study on the VERAFEYE system**Study Objective:** The objective of the study is to collect data on the usability and integration of the VERAFEYE System in

- standard of care catheter-based ablation treatments for Typical Atrial Flutter (AFL) or Atrial Fibrillation (AF)
- standard of care left atrial appendage (LAA) closure procedures
- standard of care atrial septal defect (ASD) closure procedures

Results from this study will be used to guide development and refinement the VERAFEYE System.

Indication for Use: The VERAFEYE System is indicated for intracardiac and intraluminal ultrasound visualization of cardiac and great vessel anatomy and physiology as well as visualization of other devices in the heart and great vessels of patients.**Clinical Investigation Device:** VERAFEYE System, comprising of

- **VIC** - VERAFEYE Imaging Catheter
- **CIU** - Catheter Interface Unit
- **SC** – System Console

Control Device: NA**Study Design:** The LUMINIZE study is a prospective, non-randomized, single-arm feasibility study.

**LUMINIZE_CLINICAL PROTOCOL**Document ID: VER-DOC-527
Controlled Document: VER-SIGN-3084TEMPLATE:
ONEPROJECTS/SIGN-267

Version: 4.0

Project: VERAFYE (VER)
Date: 22-Nov-2024 14:16:10
Page: 8 / 51

Planned Number of Subjects: Enrolment will be considered as complete when 40 subjects have completed the ablation, or LAA/ASD closure procedure with the VERAFYE System as imaging system.

Planned Number of Sites/Countries: Up to 2 sites in Ireland may participate in this study.

Study Endpoints: This is a feasibility study and no formal endpoints or hypothesis testing are planned in the study. The study is not designed to collect data for product approval and as such does not have a safety or efficacy endpoint.

Inclusion Criteria:

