5.7. STUDY DESIGN

This is a prospective, non-randomized, single-arm feasibility study. This study is a pilot stage study according to ISO/FDIS 14155: 2020 (E) - Annex I. Results from this study will be used to guide development and refinement of the VERAFEYE System.

The study is designed to assess the usability and integration of the VERAFEYE System in standard of care, catheter-based ablation treatments for Typical Atrial Flutter (AFL) or Atrial Fibrillation (AF), standard of care left atrial appendage closure (LAAC) procedures and standard of care atrial septal defect (ASD) closure procedures. Results from this study will be used to guide development and refinement the VERAFEYE System.

Intended Users of the VERAFEYE System are interventional cardiologists and electrophysiologists who are trained in percutaneous and transseptal procedures and who have completed the VERAFEYE System training. The VERAFEYE System training is offered by the Sponsor. The VERAFEYE System should only be performed by these Intended Users.

A prospective study design will ensure that identical procedures are followed for data capture and review.

Up to 4 operators per site will be allowed to perform study procedures, unless written approval from LUMA Vision was obtained.

A sample size of 40 subjects was chosen to allow for sufficient feasibility testing and data collection for the ablation, LAA and ASD closure procedures. The sample size is not statistically based but is based on a reasonable number of data sets to assess the images collected with the VERAFEYE System.

In protocol rev 4.0, the sample size was extended from 20 subjects to 40 subjects, in order to collect more clinical data for further system development and to ensure the collection of information from different operators.

Enrolment in this study is competitive, there is no limit of enrolments per site.

Subject procedures will follow a sequential pattern (one site after the other) to allow LUMA Vision field support personnel to be present during the procedures and to ensure the availability and installation of necessary equipment.

[figure not shown]
Enrolment in the study is expected to be completed in approximately 6 months. The follow-up for each participant is expected to be approximately 7 days, therefore the total study duration is expected to last approximately 7 months.

**LUMINIZE_CLINICAL PROTOCOL**Document ID: VER-DOC-527
Controlled Document: VER-SIGN-3084TEMPLATE:
ONEPROJECTS/SIGN-267

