**LUMINIZE_CLINICAL PROTOCOL**

Document ID: VER-DOC-527
Controlled Document: VER-SIGN-3084

Study enrolment will be considered as complete when 40 procedure subjects have been enrolled (see section 'subject classification').

Enrolment in the study is expected to be completed in approximately 6 months. The follow-up for each participant is expected to be approximately 7 days, therefore the total study duration is expected to last approximately 7 months.

Up to 2 sites in Ireland may participate in the study. Enrolment in this study is competitive, there is no limit of enrolments per site.

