5.14.8. PROTOCOL DEVIATIONS

No deviations from the protocol are allowed, except to protect the rights, safety, and well-being of human subjects under emergency circumstances. In that event, the Investigator will notify Sponsor immediately in writing. The Investigator will also inform their EC of all deviations according to Institutional requirements. In the event of any deviation from the clinical protocol, a deviation CRF will be completed. The occurrence of clinical investigation plan deviations will be monitored by the Sponsor on an ongoing basis.

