5.14.9. PROTOCOL AMENDMENTS

Any amendment to the protocol will require review and approval by the EC, and regulatory authority (as applicable) before the changes are implemented to the study.

**LUMINIZE_CLINICAL PROTOCOL**Document ID: VER-DOC-527
Controlled Document: VER-SIGN-3084TEMPLATE:
ONEPROJECTS/SIGN-267

Version: 4.0

Project: VERAFEYE (VER)
Date: 22-Nov-2024 14:16:10
Page: 45 / 51**5.14.10. EARLY TERMINATION**

The Sponsor retains the right to terminate the study at any time after carefully weighing the benefits against any possible risks. In case of early termination of the study, the Sponsor will promptly inform the Principal Investigators, Ethics Committee and regulatory authorities, as applicable. The Sponsor shall provide the reason for early termination.

The following circumstances may justify early termination of a site:

- The investigational site fails to comply with Good Clinical Practices (GCP) standards
- The first subject fails to be recruited within a reasonable period after initiation of the investigational site
- Recruitment of subsequent subjects is unreasonably slow.

The following circumstances may justify early termination of a study:

- Occurrence of severe device-related complications in one or more subjects
- Information that is expected to be gathered by this study has already been gained by other means
- The development of the test product is discontinued by the Sponsor, or the study proves not to meet the expected goal
- Instructions from the EC or regulatory authorities to suspend or terminate the study
- Other important or unforeseen circumstances

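### Section 5.9.2 closes enrolment at 20 procedure subjects, while the synopsis, 5.7 and 5.9.1 all set 40

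*Combined protocol and SAP*

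**What the plan says.** Four places in the current text bear on the size of the study.

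- Section 5.9.2, Subject Classification: "Enrolment will be considered as complete when 20 procedure subjects have been enrolled".
- Section 5.9.1, Point of Enrolment: "Study enrolment will be considered as complete when 40 procedure subjects have been enrolled (see section 'subject classification"; the cross-reference leads to 5.9.2.
- Section 5.2, Protocol Synopsis: "Enrolment will be considered as complete when 40 subjects have completed the ablation, or LAA/ASD closure procedure with the VERAFYE System as imaging system".
- Section 5.7, Study Design: the sample size is 40, and in revision 4.0 "the sample size was extended from 20 subjects to 40 subjects, in order to collect more clinical data" and to obtain information from different operators.

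Section 5.7 adds that the number has no statistical basis, and 5.6 states that there are no formal endpoints and no hypothesis tests. Sections 5.7 and 5.9.1 both say that enrolment is competitive, without a cap per site.

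**The concern.** A closing rule is an operative instruction: it tells sites and sponsor when to stop recruiting. Here a reader who follows the pointer in 5.9.1 arrives at a section that gives half the number.

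If 5.9.2 is followed, the study ends before the additional data and operator experience that justified the extension have been collected. If 5.9.1 and the synopsis are followed, subjects 21 to 40 have an investigational catheter passed to the heart through the femoral vein (5.4.2) after one section of the same protocol has declared enrolment complete. Section 5.14.8 is strict: "No deviations from the protocol are allowed, except to protect the rights, safety, and well-being of human subjects under emergency circumstances". The status of those subjects should not be open to argument.

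**Working it through.** There is no sample-size formula to reproduce, because the protocol gives no significance level, power, effect size or margin. The check is a comparison of the statements, followed by simple arithmetic.

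**Statements side by side**

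| Place | Number | What is counted |
|---|---|---|
| 5.2 Synopsis | 40 | subjects who have completed the procedure with the system |
| 5.7 Study Design | 40 (raised from 20) | subjects |
| 5.9.1 Point of Enrolment | 40 | procedure subjects |
| 5.9.2 Subject Classification | 20 | procedure subjects |

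**Can the two numbers be reconciled?**

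1. *Different unit?* No. Sections 5.9.1 and 5.9.2 both count procedure subjects. Section 5.9.2 defines these as participants who undergo the procedure with the VERAFEYE System as imaging system, which is in substance what the synopsis counts.
2. *Different scope?* No. The sentence in 5.9.2 names no site, procedure type, cohort or stage, and a quota of 20 per site would conflict with the absence of any site cap.
3. *Superseded text?* No. The sentence stands in the body of version 4.0. The version history in section 4 lists 5.9.2 among the sections updated to 40. That agrees with a missed edit, but the finding does not depend on it.

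**Size of the gap**

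- 40 − 20 = 20 subjects; 20/40 = 50% of the stated size.

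**Against the stated reason of different operators**

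- Up to 2 sites (5.2, 5.9.1). Section 5.7: "Up to 4 operators per site will be allowed to perform study procedures", unless the sponsor approves otherwise in writing.
- Maximum without such approval: 2 × 4 = 8 operators.
- With 8 operators and an even split (assumed): 20/8 = 2.5 procedures each, against 40/8 = 5.
- With 4 operators and an even split (assumed): 20/4 = 5 procedures each, against 40/4 = 10.

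**Illustration of the information lost** (not a planned analysis)

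If no event of a given type is seen in n subjects, the exact two-sided 95% upper limit for its rate is 1 − 0.025^(1/n):

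- n = 20: 1 − 0.025^(1/20) = 0.168, or 16.8%
- n = 40: 1 − 0.025^(1/40) = 0.088, or 8.8%

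With the one-sided 95% convention, 1 − 0.05^(1/n), the limits are 13.9% and 7.2%. Under either convention the limit is nearly twice as high at 20 as at 40.

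**The case against.** The strongest reply is that the document largely resolves the conflict itself. Section 5.7 says in plain text that the size went from 20 to 40 and why, so a careful reader can recognise the 20 as the old figure. The study is descriptive, so no inference, power figure or stated safety rule changes. This stands, and it limits the consequence. It does not make the sentence in 5.9.2 correct, and a closing rule should not have to be interpreted by reference to another section.

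A second reply is that 5.14.8 places its duties mainly on the investigator, whereas closing enrolment is in practice a decision for the sponsor, who may terminate the study at any time under 5.14.10. The protocol does not say that stopping early, or continuing to 40, is a deviation. This also has force: stopping at 20 could be handled as early termination. The contradiction is enough without a claim that either course is a deviation, though the uncertain status of subjects 21 to 40 remains.

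Third, the per-operator counts and upper limits rest on assumptions or conventions that the protocol does not set. That is correct. They show scale only; the figures taken from the document are 20 and 40.

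**Conclusion.** The concern holds. Section 5.9.2 is wrong as written: it closes enrolment at half the number given in the synopsis, 5.7 and 5.9.1, and no reading of unit, scope or stage reconciles them. The intended number is 40, since 5.7 both sets it and explains the change from 20. The consequence is operational. It concerns when recruitment stops and the standing of up to 20 subjects; it does not touch error rates, power or the analysis method. The conclusion itself needs no assumption. Only the per-operator figures (even split, 4 or 8 operators) and the zero-event limits do. The sentence must be corrected because it governs how many people are exposed to an investigational device.

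**What to change.** In 5.9.2, replace 20 with 40 in the sentence on completion of enrolment. The synopsis, 5.7, 5.9.1 and 5.9.2 then agree. Leave the synopsis wording as it is: completion of the procedure is the clearer trigger, because the protocol elsewhere defines enrolment as signature of the consent form. If Figure 4 or Figure 5 shows an enrolment number, check it at the same time.

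The edit is one number. Section 5.14.9 sets the cost: "Any amendment to the protocol will require review and approval by the EC, and regulatory authority (as applicable) before the changes are implemented". There is no change to design, data collection or analysis, and no subject is added beyond the 40 already stated.
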